**3. OBJECTIVES AND ENDPOINTS**

Objectives	Endpoints
Primary	

 
To assess the safety and tolerability of a single dose of ERX-963 vs. placebo in patients with DM1
 
	
 
The proportion of participants with adverse events, serious adverse events (SAEs), and drug related adverse events
 

Secondary	

 
To assess the effect of intravenously-administered ERX-963 vs. placebo on sleepiness, vigilance, and working memory in patients with DM1
 
	Repeated measurements of the following: 
 
Stanford Sleepiness Scale (SSS) score
 
Psychomotor Vigilance Task (PVT) – No. of lapses and 1/Longest 10% Response time (1/RT) and median reaction time
 
One-back task – proportion of correct response
 
Clinical Global Impression – Improvement scale (CGI-I)
 
Patient Global Impression – Improvement scale (PGI-I)
 

Exploratory	

 
To correlate ERX-963 plasma concentrations to clinical efficacy endpoints in patients with DM1
 
To assess the effect of intravenously-administered ERX-963 vs. placebo on brain activity in patients with DM1
 
	Repeated measurements of the following: 
 
Plasma ERX-963 concentration
 
Stanford Sleepiness Scale (SSS) score
 
Psychomotor Vigilance Task (PVT) – No. of lapses and 1/Longest 10% Response time (1/RT) and median reaction time
 
One-back task – proportion of correct response
 
EEG – theta/alpha and theta/beta spectral ratios, and theta, alpha, and beta percentages
 

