##### Events Meeting the AE Definition

- Any abnormal laboratory test results (hematology, clinical chemistry, or urinalysis) or other safety assessments (eg, ECG, radiological scans, vital signs measurements), including those that worsen from baseline, considered clinically significant in the medical and scientific judgment of the investigator (ie, not related to progression of underlying disease).
- Exacerbation of a chronic or intermittent pre-existing condition including either an increase in frequency and/or intensity of the condition.
- New conditions detected or diagnosed after study intervention administration even though it may have been present before the start of the study.
- Signs, symptoms, or the clinical sequelae of a suspected drug-drug interaction.
- Signs, symptoms, or the clinical sequelae of a suspected overdose of either study intervention or a concomitant medication. Overdose per se will not be reported as an AE/SAE unless it is an intentional overdose taken with possible suicidal/self-harming intent. Such overdoses should be reported regardless of sequelae.

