**Follow-up of AEs and SAEs**

- The investigator is obligated to perform or arrange for the conduct of supplemental measurements and/or evaluations as medically indicated or as requested by sponsor/designee to elucidate the nature and/or causality of the AE or SAE as fully as possible. This may include additional laboratory tests or investigations, histopathological examinations, or consultation with other health care professionals.
- If a participant dies during participation in the study or during a recognized follow-up period, the investigator will provide medical monitor with a copy of any post-mortem findings including histopathology.
- New or updated information will be recorded in the originally completed CRF.
- The investigator will submit any updated SAE data to the sponsor within 24 hours of receipt of the information.

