#### 4.2 Summarization of Data

Study results will be summarized by treatment group [for example., A, B, or C] or by treatment sequence [for example, A-B, B-A, A-C, C-A] unless otherwise specified.

No imputation of missing data will be performed. No windowing of visits will be performed unless otherwise specified.

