## **12 SAFETY ANALYSES**

### **12.1 Adverse Events**

Adverse events will be coded using the Medical Dictionary for Regulatory Activities (MedDRA) coding system (using the MedDRA Version stated in Data Management Plan). An overall summary table will be presented by treatment group that summarizes all treatment-emergent adverse events (TEAEs), all serious TEAEs, all drug-related TEAEs, number of deaths, and all severe TEAEs for the safety population. In addition, frequency tables will be presented by treatment group for all TEAEs, for all drug related adverse events, and for all adverse events resulting in discontinuation from study, by system organ class and preferred term for the safety population. The frequency tables will be ordered by system organ class. Subject listings of all TEAEs, serious TEAEs, and drug related TEAE will also be provided.

In all displays, TEAEs will be displayed by MedDRA System Organ Class and Preferred Terms, with patients who have the same TEAE counted only once for that event and with patients who have more than one TEAE within a System Organ Class counted only once in that System Organ Class.

Pretreatment adverse events are defined as those events which occur between time of signing the informed consent and the first dose of study medication. Pretreatment AEs will be listed separately from the TEAEs.

Treatment-emergent AEs will include AEs which start between the date and time of study drug dosing and through Study Day 2, within each period.

All TEAEs will be listed by treatment sequence, subject, and timing of event. Treatment taken just prior to the event will be provided in the listing.

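### SAP 12.1 defines treatment-emergent events by start time only, so an event that begins before a dose and worsens after it can be missing from that period's treatment column

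*SAP*

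**What the plan says.** The primary endpoint in Protocol Section 3 is "The proportion of participants with adverse events, serious adverse events (SAEs), and drug related adverse events". It is not limited to treatment-emergent events.

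The SAP makes that limitation. Section 12.1 builds the overall summary on treatment-emergent events, and the titles of the four planned adverse event tables (14.3.1.1 to 14.3.1.4) all carry the same restriction. Its test is: "Treatment-emergent AEs will include AEs which start between the date and time of study drug dosing and through Study Day 2, within each period". Events before the first dose form a separate class, "Pretreatment adverse events are defined as those events which occur between time of signing the informed consent and the first dose of study medication", and "Pretreatment AEs will be listed separately from the TEAEs".

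Protocol 10.3.1 is wider about what an adverse event is. It includes "Exacerbation of a chronic or intermittent pre-existing condition including either an increase in frequency and/or intensity of the condition" and also "New conditions detected or diagnosed after study intervention administration even though it may have been present before the start of the study". On record keeping, the follow-up part of Protocol 10.3.3 says "New or updated information will be recorded in the originally completed CRF". SAP 4.2 adds "No imputation of missing data will be performed".

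**The concern.** A symptom that is mild before the infusion and severe after it is a tolerability signal, and the protocol treats it as an adverse event. The SAP asks only when the event began. If the database holds one row with a pre-dose start, the participant does not appear under the treatment that preceded the worsening.

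The design makes such events plausible. Events are collected from consent, and screening may run up to 21 days before the first dose. On each dosing day, the EEG is attached, two IV lines are placed and two test batteries are run before the infusion. Protocol 2.2 names dizziness, injection site pain and agitation among the frequent drug-related events, and any of these could begin during those procedures and intensify later.

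The primary endpoint is a proportion read by treatment in very small groups, so the classification of one participant is visible. SAP Section 11 shows that the authors considered the same issue for medications: it has an explicit rule for those started earlier and still in use at dosing. Events have no such rule.

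**Working it through.** **No figure to reproduce.** The primary endpoint is descriptive. The plan states no event rate, margin or sample-size calculation for it. The check is therefore a reading of the rule case by case, followed by the weight of one participant.

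**Cases.** I take the dosing day as Study Day 1 of its period. The washout is counted from Period 1 dosing and lasts about 4 days or more, so the Period 2 dose falls after the Period 1 window has closed. In cases 1 to 4 the event is still open at a later dose and worsens after it, and the worsening is kept on the existing row.

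| Case | Recorded start | Result under SAP 12.1 |
|---|---|---|
| 1 | Screening | Pretreatment; listed only |
| 2a | Pre-dose procedures, Period 1 | Pretreatment; listed only |
| 2b | Pre-dose procedures, Period 2 | Neither pretreatment nor treatment-emergent |
| 3 | After Study Day 2 of Period 1, before the Period 2 visit | Neither pretreatment nor treatment-emergent |
| 4 | Inside the Period 1 window, worsening after the Period 2 dose | Counted under the Period 1 treatment only |

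Cases 2b and 3 have no category because pretreatment means before the first dose, while the Period 1 window has ended and the Period 2 window has not opened.

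In case 4 a placebo-first participant whose event worsens on ERX-963 appears only in the placebo column. An ERX-963-first participant whose event worsens on placebo appears only in the ERX-963 column.

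**The same events under the other recording choice.** If the worsening is entered as a new adverse event dated to the worsening, all five rows start inside a dosing window and count for that period. The tabulated result thus turns on a data-entry convention that neither document gives.

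**Weight of one participant.** Shift = 100/n percentage points:

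- n=6 (minimum evaluable per cohort): 100/6 = 16.7
- n=12 (two cohorts of 6): 100/12 = 8.3
- n=14 (estimated completers): 100/14 = 7.1

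For scale, moving from 0/6 to 1/6 changes the exact (Clopper-Pearson) 95% interval from 0 to 45.9% into 0.4 to 64.1%.

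The any-event row shifts only if the participant has no other treatment-emergent event in that period. The row for the particular preferred term shifts whether or not there are other events of a different term.

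**The case against.** The best reply is that the protocol already supplies the missing limb. Its definition of an adverse event covers exacerbated as well as new conditions, and 10.3.1 makes an exacerbation an event in its own right. A site may therefore record a post-dose exacerbation as an event that starts then, and it would count. Protocol 10.3.3 says where follow-up information goes; it does not say that the old start date is kept. This stands, and it makes the omission conditional.

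Several stronger readings are tempting and are not supported:

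- **All such events are lost.** They are not. A worsened medical-history condition counts if dated to the worsening, and a condition first detected after dosing counts if dated to its detection. Pretreatment events are listed, and Listing 16.2.7.1 gives events by patient, so nothing leaves the record. But the endpoint is a tabulated proportion, and a listing does not correct it.
- **A dosing-day event without a clock time is excluded.** No passage says so. The date and time in SAP 12.1 belong to dosing, and the ban on imputation does not address classification. The handling is simply unstated. An event dated to Study Day 2 needs no clock time.
- **Every adverse event table is restricted by the text of 12.1.** That text describes the drug-related and discontinuation tables without the restriction; the table titles impose it.
- **The ERX-963 proportion is understated by a calculable amount.** That would need the share of participants with an open event at dosing, the share of those who worsen, and the share with another new event. The documents give none of these, and the calculation would also assume that every worsening stays on the old row.
- **The comparison is biased toward safety.** Placebo periods follow the same rule. The direction depends on whether worsening differs by treatment, which is unknown.

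**Conclusion.** The concern holds in a conditional form. Start time is the only test in SAP 12.1, and nothing in the SAP brings in an event that began before a dose and worsened after it. Where the worsening is kept on the existing row, the event is absent from that period's treatment column or, in case 4, appears only under the other treatment. Where it is entered as a new event, the present rule already captures it. Neither document says which is to be done, so a primary safety count can depend on site habit or on programming decisions.

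The size is 16.7, 8.3 or 7.1 percentage points per participant at n=6, 12 or 14. No expected bias, and no direction of bias, can be stated. This is a cheap correction worth making before unblinding. It does not undermine the study: the endpoint is not formally tested, and every event can be read individually in the listings. The missing clock time is a point for clarification only.

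**What to change.** **SAP 12.1.** Define a treatment-emergent event as one that starts, or increases in intensity, frequency or seriousness, at or after dosing and within that period's window, and attribute it to that period's treatment.

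**CRF completion.** Have a post-dose worsening entered as a new dated adverse event row, and reconcile this with the follow-up wording of Protocol 10.3.3. Both parts are needed: without a dated row, the SAP limb may have nothing to work on.

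**Clarification.** Treat an event on a dosing day with no start time as treatment-emergent for that period unless other information shows that it began before dosing. State that this is a classification rule that applies despite SAP 4.2.

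**What not to add.** Do not count every condition first detected after dosing. The Schedule of Activities places each period's laboratory sample after all assessments (footnote b), so that limb would credit pre-existing abnormalities to the treatment just given.

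**Cost.** Two sentences in the SAP and one CRF instruction. For data already entered, the cost is also a blinded check of events open at a dose, which is small with an estimated 14 completers. The proportions in both the ERX-963 and placebo columns may rise slightly, and one condition may properly appear under both treatments for the same participant.

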### **12.2 Laboratory Tests (Hematology, Serum Chemistry, and Urinalysis)**

Hematology and serum chemistry laboratory tests are collected at Screening, one time at the end of each assessment period, and at the follow-up/early termination visit. Urinalysis is collected at Screening and at the follow-up/early termination visit.

For hematology and chemistry quantitative tests, summary statistics (n, mean, SD, minimum, median, and maximum) will be presented for the observed values at Screening, end of the experimental treatment period, and end of the placebo treatment period for the safety population by treatment group. Summary statistics will also be presented for the change from baseline to the end of the experimental treatment period, and to the end of the placebo treatment period. In these displays, baseline will be defined as the sample collected at Screening.

Hematology, chemistry and urinalysis results will be displayed in subject listings, with those values falling outside the laboratory reference range flagged. Laboratory reference ranges will be provided by the laboratory site(s) and will be included in an appendix of the clinical study report.

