**1.3. Schedule of Activities (SoA)**

Procedure	Screening Visit (up to 21 days before Period 1)	Intervention Period			End of Study (4-18 days after Period 2) or Early Discontinuation
		Period 1	Washout Period: 4-18 days	Period 2	
Informed consent	X				
Inclusion and exclusion criteria	X				
Medical history (including myotonic dystrophy diagnosis history)	X				
Medication history a	X				
Full physical examination and Demography including height and weight	X				
Brief physical exam		X b		X b	X
Vital signs (BP, Respiration Rate and Pulse Rate)	X	X c		X c	X
Laboratory assessments (hematology, clinical chemistries) 	X	X b		X b	X
Hepatitis C antibody test	X				
Plasma biomarker exploration (subjects who consented to provide the sample only)	X				
Serum pregnancy test (WOCBP only)	X				X
Urinalysis	X				X
12-lead ECG	X				
Pulmonary function test with spirometry	X				
MDHI, Epworth sleepiness scale (ESS)	X				
Actigraph d	X				
Polysomnograph e	X				
Outcome Measure Tests (Stanford sleepiness scale [SSS], Psychomotor vigilance task [PVT] and One-back test)	X f	X g		X g	
Randomization		X			
Video (subjects who consented only)		X h		X h	
EEG		X h		X h	
Study intervention (IV Infusion) k		X		X	
PK sampling		X i		X i	
CGI-I and PGI-I		X j		X j	

Procedure	Screening Visit (up to 21 days before Period 1)	Intervention Period			End of Study (4-18 days after Period 2) or Early Discontinuation
		Period 1	Washout Period: 4-18 days	Period 2	
AE review	X	X	←=====→		
Concomitant medication review		X	←=====→		

- a Prescription and non-prescription (over the counter, OTC) medications, herbal medications, vitamins, minerals and medications over the past 30 days. Lifetime history of medication taken for DM1 or sleep.
- b After completion of all assessments (after PGI-I is completed).
- c Pre-dose vital signs within 60 minutes prior to start of study intervention; post-dose vital signs after completion of all assessments (after PGI-I is completed).
- d To qualify participants per [inclusion criteria #3](#).

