## 8. STUDY ASSESSMENTS AND PROCEDURES

Study procedures and their timing are summarized in the SoA ([Section 1.3](#)). Protocol waivers or exemptions must be discussed with the Expansion medical monitor.

Urgent safety concerns should be discussed with the sponsor immediately upon occurrence or awareness to determine if the participant should continue or discontinue study intervention.

Adherence to the study design requirements, including those specified in the SoA ([Section 1.3](#)), is essential and required for study conduct.

All screening evaluations must be completed and reviewed to confirm that potential participants meet all eligibility criteria. The investigator will maintain a screening log to record details of all participants screened and to confirm eligibility or record reasons for screening failure, as applicable.

Procedures conducted as part of the participant's routine clinical management (eg, blood count) and obtained before signing of the ICF may be utilized for screening or baseline purposes provided the procedures met the protocol-specified criteria and were performed within the time frame defined in the SoA ([Section 1.3](#)).

The estimated amount of planned blood collected from each participant over the duration of the study is described below. Repeat or unscheduled samples may be taken for safety reasons or for technical issues with the samples.

Blood Sample Reason	No. of Samples	Volume per Sample (mL)	Total Volume (mL)
Total PK samples in study	10	6	60
Serum pregnancy test	2	5	10
Clinical laboratory tests (hematology and clinical chemistry)	4	20	80
Hepatitis C Antibody	1	10	10
Biomarker test	1	10	10
Total Estimated Blood Volume During Entire Study (mL)			170

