### Period 1 and Period 2 Evaluation Day

- Allot randomization number (Period 1 only);
- Pre-dose Vital Signs (systolic and diastolic BP, respiration rate and pulse rate within 60 minutes prior to dosing) and brief clinical review;
- Hook up EEG and start recording;
- Place two IV lines on two separate limbs (identify one line for drug administration and the second one for blood sampling);
- Start recording video (if patient consented);
- Administer practice outcome measure tests (order of tests: SSS-PVT-One back; approximate duration of 15 minutes);
- Administer pre-dose baseline outcome measure tests (order of tests: SSS-PVT-One back; approximate duration of 15 minutes) 20 minutes after completion of practice outcome measure test;
- Administration of study intervention (at approximately the same time of day [ $\pm 1$ h] in both Period 1 and 2);
  - **Cohort 1 (1 mg) and Cohort 2 (if selected dose is 0.5 mg or 1 mg):** administer as a 5 minute infusion.
  - **Cohort 2 (if selected dose is 2 mg):** administer as a 15 minute infusion
- Administer outcome measure tests (approximate duration of 15 minutes each) starting at:
  - **Cohort 1 (1 mg) and Cohort 2 (if selected dose is 0.5 mg or 1 mg):** 15 minutes, 45 minutes, 1 hour 15 minutes and 1 hour 45 minutes after the start of IV infusion;
  - **Cohort 2 (if selected dose is 2 mg):** 25 minutes, 55 minutes, 1 hour 25 minutes and 1 hour 55 minutes after the start of IV infusion;
- Obtain blood samples (PK sampling) after conclusion of each set of outcome measure tests to measure plasma [REDACTED] concentrations:
  - **Cohort 1 (1 mg):** at the end of drug administration (5 minutes after the start of dosing) and at approximately 30 minutes, 1 hour, 1 hour 30 minutes and at 2 hours after the start of IV infusion;
  - **Cohort 2 (if selected dose is 0.5 mg or 1 mg):** at the end of drug administration (5 minutes after the start of dosing) and at approximately 30 minutes, 1 hour, 1 hour 30 minutes and at 2 hours after the start of IV infusion;
  - **Cohort 2 (if selected dose is 2 mg):** at the end of drug administration (15 minutes after the start of dosing) and at approximately 40 minutes, 1 hour and 10 minutes, 1 hour 40 minutes and at 2 hours and 10 minutes after the start of IV infusion.
  - The exact time when the blood samples were taken will be recorded.

- End video recording;
- General clinician- and patient-reported questionnaire (CGI-I and PGI-I);

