- Vital Signs (systolic and diastolic BP, respiration rate and pulse rate) after completion of all assessments;
- Brief physical examination;
- Obtain blood samples for clinical laboratory tests (hematology and clinical chemistry) at the end of the assessment period;
- Review of AEs and concomitant medications (throughout the day, continuing until the end of the study).

Subjects will be given instructions on when to return to the clinic for Period 2 (approximately 4 to 18 days after Period 1), and for End-of-Study visit (after approximately 4 to 18 days after Period 2).

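### The planned laboratory summaries cannot show, under ERX-963, a change that emerges days after dosing; a by-sequence, by-visit table including End of Study would make it visible

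*SAP*

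**What the plan says.** SAP 12.2 has hematology and chemistry drawn at Screening, "one time at the end of each assessment period, and at the follow-up/early termination visit". Protocol Section 8 (Period 1 and Period 2 Evaluation Day) places the dosing-day draw last: "Obtain blood samples for clinical laboratory tests (hematology and clinical chemistry) at the end of the assessment period". Footnote b of the Schedule of Activities agrees, putting it after the PGI-I. The last pharmacokinetic samples before it are "at approximately 30 minutes, 1 hour, 1 hour 30 minutes and at 2 hours after the start of IV infusion", or ten minutes later for a 2 mg dose. The laboratory draw therefore falls shortly after 2 hours. No pre-dose laboratory sample is taken in either period.

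SAP 12.2 asks for summary statistics of the "observed values at Screening, end of the experimental treatment period, and end of the placebo treatment period for the safety population by treatment group", plus change from baseline to the end of each treatment period. On baseline it says: "In these displays, baseline will be defined as the sample collected at Screening". End of Study values go to listings with out-of-range flags, not to the summaries.

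SAP 12.3 treats vital signs differently: baseline is the pre-dose value of each period, and every time point is summarised.

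**The concern.** Each dosing-day sample is labelled with the treatment given about 2 hours earlier, although the previous dose was given only 4 to 18 days before. An effect on a laboratory value may take longer than 2 hours to appear. In the ERX-963-first sequence the first sample able to show it is the Period 2 sample, which is tabulated as placebo. In the placebo-first sequence it is the End of Study sample, which is not tabulated. The ERX-963 column contains only 2-hour values, so a later change cannot appear in it, whereas the placebo column can carry one.

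The primary objective is safety against placebo, and Protocol 8.2 names laboratory tests among the safety evaluations. A reader who sees only the by-treatment table could take it as reassurance about the days after dosing, an interval it does not cover for ERX-963.

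**Working it through.** **Inputs from the documents**
- Four laboratory samples of 20 mL: 4 x 20 = 80 mL, as in the Protocol Section 8 blood table. The total 60 + 10 + 80 + 10 + 10 = 170 mL also reproduces. These are Screening, Period 1, Period 2 and End of Study.
- Three participants per sequence in each cohort (Protocol 4.2).
- 4 to 18 days from Period 1 to Period 2, and again from Period 2 to End of Study (Schedule of Activities).
- Half-life 40 to 80 minutes (Protocol 4.2).

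The documents state no laboratory effect size, so there is no planned figure to reproduce. The effects below are assumptions.

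**Notation.** a is the ERX-963 effect about 2 hours after dosing; d is the effect at the next visit, taken to have the same sign; r is the fraction of d left one visit later. Placebo has no effect.

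**Expected change from Screening, and where SAP 12.2 puts it**

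| Sequence | Period 1 | Period 2 | End of Study |
|---|---|---|---|
| Placebo, then ERX-963 | 0 (placebo column) | a (ERX-963 column) | d (not summarised) |
| ERX-963, then placebo | a (ERX-963 column) | d (placebo column) | r x d (not summarised) |

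**What the columns show, three per sequence**
- ERX-963: (3a + 3a)/6 = a
- Placebo: (3 x 0 + 3d)/6 = d/2
- Apparent gap: a - d/2, which changes sign when d > 2a

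Examples in arbitrary units:

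| a | d | ERX-963 | Placebo | Gap |
|---|---|---|---|---|
| 0 | 10 | 0 | 5 | -5 |
| 2 | 10 | 2 | 5 | -3 |
| 5 | 10 | 5 | 5 | 0 |
| 5 | 5 | 5 | 2.5 | +2.5 |
| 5 | 0 | 5 | 0 | +5 (no distortion) |

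**Unequal sequences.** If f is the share receiving ERX-963 first, the gap is a - f x d, which reverses when d > a/f. With two placebo-first and four ERX-963-first, f = 4/6 and the threshold is 1.5a. With four and two, f = 2/6 and the threshold is 3a.

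**Period adjustment does not help.** Averaging the within-participant differences over sequences gives [(a - 0) + (a - d)]/2 = a - d/2, the same result.

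**The Screening baseline is not the cause.** For a participant with both samples, (ERX-963 value - Screening) - (placebo value - Screening) = ERX-963 value - placebo value. Screening cancels. The gap arises from which sample is tabulated under which treatment, and from leaving End of Study out.

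**What a by-sequence, by-visit table would show**
- Period 1, ERX-963-first minus placebo-first: a - 0 = a, free of carryover.
- Period 2, same contrast: d - a.
- End of Study, placebo-first minus ERX-963-first: d - r x d.
- Mean of the last two: d - (a + r x d)/2. For a = 0 and d = 10 this is 10 (r = 0) or 7.5 (r = 0.5), against -5 in the planned layout. For a = 2 and d = 10 it is 9 or 6.5, against -3.

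The next-visit values are not a clean placebo-controlled estimate of d, because the comparison group has itself received ERX-963 by then. They do make d visible.

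**The case against.** The strongest reply is that a delayed effect is hypothetical. Protocol 4.2 regards the washout as ample for both drug and effects. Four days is 5,760 minutes, or 72 to 144 half-lives, and the adverse effects listed in Protocol 2.2 are neither hepatic nor hematological. This stands as a statement about likelihood. It does not exclude a downstream change that outlasts exposure, and the protocol itself collects laboratory samples 4 to 18 days after Period 2.

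It also stands that the tables are descriptive, with no planned laboratory contrast or test. Every value is listed with flags, and clinically significant abnormalities are repeated until resolved (Protocol 8.2.4). With an estimated 14 completers, the listings can be read in full. SAP 4.2 allows summaries by sequence in general, but SAP 12.2 specifies treatment group for these.

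Three stronger readings are tempting and not supported:
- A reader might infer that the table points the wrong way for any delayed effect. It does so only when d exceeds 2a with equal sequences. An effect that resolves before the next visit is missed, not credited to placebo.
- A reader might blame the Screening baseline. It cancels, as shown above.
- A reader might infer that ERX-963 events will enter the primary adverse event proportions under placebo. SAP 12.1 says "Treatment taken just prior to the event will be provided in the listing", but that describes a listing column. A laboratory value becomes an adverse event only on the investigator's judgement (Protocol 10.3.1), and the documents do not say how its onset would be dated. An abnormality first found after the Period 2 dose could fall inside that period's treatment-emergent window, and one first found at End of Study would fall outside both windows. This is a possibility, not a planned misallocation.

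**Conclusion.** The point holds as a limit of the planned display. Under SAP 12.2 the ERX-963 summary covers only about the first 2 hours after dosing. The later samples are either tabulated under the other treatment or not summarised. If an effect a at 2 hours and d at the next visit existed, equal sequences would show a - d/2: an understatement, with the sign reversed if d > 2a.

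This rests on an effect that persists to the next visit, for which the documents give no evidence. It does not show that any actual laboratory result is wrong. Nor can it be confirmed that a laboratory summary table was kept after the April 2020 memo: the highlighting that marks removed outputs is not legible in the text available, and the table entries that can be read stop at adverse events. The conclusion therefore rests on the wording of SAP 12.2. The correction is worth making because it is cheap and closes a gap in the primary safety description.

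**What to change.** In SAP 12.2, add for each quantitative hematology and chemistry test a summary of observed values and change from Screening by treatment sequence (A-B, B-A, A-C, C-A) and visit (Screening, Period 1, Period 2, End of Study). Add a footnote that the Period 1 columns give the comparison free of carryover, and that the Period 2 and End of Study columns also hold the next-visit values for the preceding dose. If treatment codes have already been opened, label the table post hoc.

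The cost is one extra descriptive table on samples already planned. Its cells are small, three participants per sequence per cohort, and the Period 1 comparison is between participants, so it should be read as description.

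A pre-dose sample in Period 2 is optional and relevant only if dosing is still to come. It would need a protocol amendment, would take total blood volume from 170 to 170 + 20 = 190 mL, and would leave mixed baselines if some participants have already been dosed. If laboratory abnormalities are ever to be attributed to an earlier treatment, that rule must first be reconciled with the treatment-emergent window in SAP 12.1, which ends at Study Day 2 of each period.
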